#### 3.2. General Selection Criteria

To be included in the study, participants must meet the following inclusion criteria and none of the exclusion criteria.

##### 3.2.1. Inclusion Criteria

- Male or non-pregnant female; age 18 to 90
- Absence or presence of any medical history or any signs or symptoms of any disease
- Women of childbearing potential (WOCBP) must have a negative urine pregnancy test (UPT) at all visits.

##### 3.2.2. Exclusion Criteria

- Unwillingness or inability to participate in the study
- Unwillingness or inability to provide written Informed Consent Form
- WOCBP with positive pregnancy test at enrollment or at any visit

##### 3.2.3 Participant withdrawal criteria

A participant may be withdrawn from the study prior to completion for any of the following reasons:

- Adverse Event (AE)
- Death
- Physician decision
- Pregnancy at any visit
- Protocol deviation
- Other (e.g., any reason that may affect the outcome of the study or safety of participants)
- Participant no longer wants to participate (without penalty)

When a participant is withdrawn from the study for an AE (as defined in Section 5), when possible, the participant should be followed until resolution or stabilization of the AE.

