## Protocol Synopsis

Study Title: A Prospective, Non-Randomized, Multi-Center Observational Study to Establish a Physical Baseline Profile for Individual Study Subjects Using Various Modalities and Identify Deviations via Longitudinal Monitoring that May Develop Over Time and May be Relevant to Human Health and Longevity.	
Short Title	PUER Research Clinical Study
Study Type	This is a minimal-risk, prospective, non-randomized, multi-center population based observational study to establish a physical baseline profile for individual study subjects using various modalities and identify deviations through longitudinal monitoring that may develop over time and may be relevant to human health and healthy longevity.
Study Description	
The three key elements of the Puer Research protocol include (1) Medical history and physical exam (PE), (2) molecular and laboratory profiling and (3) non-invasive imaging and wearables/ “quantified self” measurements. The medical history and PE will consist of a comprehensive medical history and physical examination, administered by a trained Research Associate. Laboratory assessments will be conducted using peripheral blood samples, and potentially urine, stool or saliva samples. Non-invasive imaging assessment will consist of magnetic resonance imaging (MRI) and computerized tomography (CT) scans. Other functional assessments, including respiratory, cardiac and other functions, as well as self-quantifiable assessments via wearables will also be conducted.
 
The study will result in longitudinal real world data collection to inform if any modalities employed here can inform of baseline deviations for individuals. Researchers at study sites will not be blinded to the data being collected during this study.

Study Sites	This study will be conducted in up to 20 study sites in the United States.
Study Population	The study will be conducted in up to 10,000 participants.
Study Duration	72 months
Enrollment Duration	36 months

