### 3. Study Design

This is a prospective, population-based observational study. Participants may be recruited from clinical sites that are actively participating in the Puer Research comprehensive evaluation model. Participants and all participating health care providers are unblinded.

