### 5.3. Reporting

The Puer study does not prescribe any pharmaceutical or medical device-based intervention. Any AEs are associated with blood draw/venipuncture and MRI examinations that may or may not include Gadolinium-based contrast agents will be reported.

Each patient will be observed and queried in a nonspecific fashion at each contact during the study for any new or continuing symptoms since the last contact. All adverse events will be reported on the appropriate CRF. Details will include the type of event, date of onset, duration, intensity, causality relationship to the study procedure (if applicable), and outcome. Wherever possible, a diagnosis rather than symptom(s) will be reported.

If an AE should occur, every attempt will be made to obtain as much information as possible about event evaluation and outcome. Documents of this follow-up will be maintained with the patient's study records.

If a SAE occurs, the participation in the study will be interrupted or discontinued at the investigator's discretion.

All protocol deviations will be reported to the WCG IRB.

All SAEs will be reported immediately to the WCG IRB and the FDA (if applicable).

Endpoints will be adjudicated by the Principal Investigator. A written report detailing the endpoint adjudication will be provided by the Principal Investigator.

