## 7. Statistical Considerations

By design, the study will not employ formal hypothesis testing. Study endpoints will be described using descriptive statistics, using means and standard deviations, medians with inter-quartile ranges, and other descriptive statistical methods, as appropriate.

Data from participants who discontinue the study prior to completion will only be considered through the date of withdrawal and will not be followed in the remaining longitudinal study endpoints.

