### **8.4. Protocol Interpretation and Compliance**

The procedures defined in the protocol will be carefully reviewed by the Investigator and research staff prior to the time of study initiation to ensure appropriate interpretation and implementation. No deviations from the protocol will be acceptable. Any changes to the protocol in the form of an amendment must be submitted to Puer Research.

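### Withdrawal grounds in Section 3.2.3 are open enough for unblinded staff to apply to a participant's findings, and Section 7 then ends endpoint follow-up, so later deviation counts could be selected on outcome

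*Protocol*

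**What the plan says.** Section 3.2.3 opens permissively: "A participant may be withdrawn from the study prior to completion for any of the following reasons". The list contains adverse event, death, physician decision, pregnancy, "Protocol deviation", participant choice, and a residual ground worded "Other (e.g., any reason that may affect the outcome of the study or safety of participants". It sets no severity threshold for a deviation. For the residual ground it gives neither a criterion nor a decision-maker.

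The Synopsis states: "Researchers at study sites will not be blinded to the data being collected during this study". Section 3 adds: "Participants and all participating health care providers are unblinded". Section 5.3 states: "Endpoints will be adjudicated by the Principal Investigator".

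Section 5.4 has out-of-range laboratory markers and clinical evaluations recorded as adverse events. Section 2.2 makes the number of new deviations from the participant's own baseline the main endpoint at 12 months, with further counts at 6, 18 and 24 months and by modality.

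Section 7 says that data from participants who discontinue "will only be considered through the date of withdrawal and will not be followed in the remaining longitudinal study endpoints". The only follow-up after withdrawal that Section 3.2.3 provides for is of an adverse event, where possible, until it resolves or stabilises.

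**The concern.** The study has one cohort, no study treatment and no hypothesis test. Its result is a set of descriptive counts, so who contributes to each count matters more than anything else in the analysis.

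Three grounds for withdrawal can touch the outcome:

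- The residual ground refers to an effect on the study's outcome, without saying whether that means study integrity or a participant's results.
- The deviation ground has no threshold, although visit windows of one month either side and an extensive imaging schedule make minor deviations foreseeable.
- The adverse-event ground overlaps with the endpoint, because an out-of-range result is an adverse event under Section 5.4 and may also be a deviation from baseline.

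If any of these is applied to people because of what has been found in them, the participants who remain at 12, 18 and 24 months are no longer representative of those enrolled. A larger sample does not reduce that bias. A statistical analysis plan could describe the attrition or bound its effect, but it could not restore assessments that the protocol says will not be made.

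**Working it through.** The protocol gives no withdrawal rate, no expected number of deviations and no sample-size derivation, so it has no figure to reproduce. The check has two parts.

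**Reading the sections together**

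1. Can withdrawal be decided with the outcome in view? Section 3.2.3 makes it discretionary, and the Synopsis and Section 3 leave everyone unblinded. Section 3.2.3 does not name who decides. That site staff do so is an inference from its physician-decision ground and from Section 5.3, which leaves discontinuation after a serious adverse event to the investigator's discretion.
2. Can a finding be a ground? By the most direct route, yes: out-of-range result, then adverse event (Section 5.4), then withdrawal ground (Section 3.2.3). Under the residual ground, it can if the phrase about the study's outcome is read broadly.
3. What is lost? Under Section 7, every endpoint assessment after withdrawal. Earlier assessments are kept.

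**Size under assumed inputs**

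Let *f* be the fraction of enrolled participants removed before a timepoint, *m* the mean count in those remaining, and *km* the mean that the removed would have had. Both *f* and *k* are assumptions.

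True mean = (1 − f)m + fkm = m[1 + f(k − 1)], so observed/true = 1/[1 + f(k − 1)].

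- f = 5%, k = 2: 1/1.05 = 0.952, which is 4.8% too low.
- f = 10%, k = 3: 1/1.20 = 0.833, which is 16.7% too low.
- f = 10%, k = 0.5: 1/0.95 = 1.053, which is 5.3% too high.

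A simulation lets withdrawal at 6 months depend on the 6-month count. It assumes Poisson counts with a mean of 1 or 2 new deviations per 6 months and gamma frailty with variance 0.25, 0.5 or 1.0, in 1,000,000 people per setting. High means more than 2 deviations at 6 months (mean 1) or more than 3 (mean 2), which covers 9.9% to 19.7% of people. The cumulative 12-month mean in those remaining is compared with that in all enrolled.

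| Withdrawal in high-count group / in the rest | Overall withdrawal | Error in 12-month mean |
|---|---|---|
| 10% / 10% | 10% | about 0 |
| 20% / 5% | 6.5% to 8.0% | 2.4% to 5.3% too low |
| 30% / 5% | 7.5% to 10.0% | 3.9% to 9.2% too low |
| 50% / 5% | 9.5% to 13.8% | 7.3% to 17.1% too low |

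The error comes from the dependence on counts, not from the amount of withdrawal: 10% withdrawal unrelated to counts produces essentially none.

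**The case against.** The strongest reply is that the residual ground is only an example under a catch-all, and that a reason affecting the study's outcome most naturally means a threat to study integrity. A participant's deviation count is the outcome, not something acting on it. Removing people for having findings would also defeat a study that sets out to detect them and that admits people with any medical history or disease. This is a fair reading and may well be what was intended. A reader might infer that anyone with many findings qualifies for removal; the text does not say so. What stands is that the phrase does not exclude that use.

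A reader might also take Section 8.4, "No deviations from the protocol will be acceptable", to mean that a deviation leads to removal. It does not. It is a statement about site compliance, Section 3.2.3 is permissive, and the response that Section 5.3 requires to a deviation is a report to the IRB. Nor is an incomplete imaging visit clearly a deviation, since much of the imaging is conditional on history, examination or risk. The protocol also offers no evidence that deviations are commoner in people who become ill.

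Two safeguards count in the plan's favour. Data up to withdrawal are kept, and Section 6.1 includes a withdrawal form in the CRF, so reasons can be tabulated. That could show whether withdrawal was selective. It could not supply the missing counts.

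Finally, the deviation ground has a legitimate use where consent was invalid or the participant was ineligible at enrolment. Deleting it outright would go too far.

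**Conclusion.** The point holds as a weakness in stated rules, not as a demonstrated bias. Section 3.2.3 leaves withdrawal open to outcome-related use by people who see the data, Section 5.4 adds a direct route from an abnormal result to a withdrawal ground, and Section 7 makes the loss permanent. What is exposed is the counts at timepoints after withdrawal, including the 12-month main endpoint for anyone withdrawn before then, and the corresponding counts by modality. Since nothing is tested and no arms are compared, a type I error or a treatment contrast is not at issue.

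A reader might take the percentages as estimates for this study. They are hypothetical: the withdrawal fractions, the count ratios and the simulation model are all assumed, and the direction reverses if participants with few findings are the ones removed. They show only that selective withdrawal of modest extent could move a mean count by several percent. The change is cheap and works only before participants are lost, so it should be made.

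**What to change.** In Section 3.2.3:

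- Delete the part of the residual ground that refers to an effect on the study's outcome, and leave the participant-safety part.
- Limit the deviation ground to invalid consent or ineligibility at enrolment. Flag all other deviations, and keep those participants and their completed assessments in follow-up and analysis.
- Leave participant choice, death and the other grounds in place.

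In Section 7, state that stopping some study procedures, whether for an adverse event, a physician's decision or a deviation, does not end endpoint follow-up. Remaining assessments that the participant consents to, and that the investigator does not rule out for safety, are still collected and counted. This addition is needed because editing the two grounds alone would leave the adverse-event and physician-decision routes open and the loss of later data unchanged.

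The cost is a short amendment with IRB review. The downside is that some off-window or incomplete visits stay in the data set and must be flagged.

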### **3.3. Study Procedures**

#### **3.3.1. Study Design**

- This is a prospective, population-based observational study. Participants may be recruited from clinical sites that are actively participating in the PUER Research™ Comprehensive Evaluation protocol. Participants and all participating health care providers are unblinded.
- The three key elements of the PUER Research protocol include (1) Medical history and PE, (2) molecular and laboratory profiling and (3) non-invasive imaging, with the option of adding functional assessments and wearables/quantified self-assessments, as determined by the Medical history and PE.

#### **3.3.2. Methodology**

Each of the visits include a combination of Medical history and PE, biochemical and “omics” assessments, non-invasive imaging assessments and optional functional assessments and wearables and quantified self-assessments.

*Medical history and PE* The Medical history and PE consists of a comprehensive “History and Physical Examination”, administered by a trained Research Associate. The elements of the history and physical examination are recorded in the Case Report Form (CRF).

- *Pregnancy Testing*

Pregnancy testing consists of a UPT for all WOCBP. The results must be negative for the subject to be able to participate in each visit.

- *Genomic Analysis*

- Whole genome sequencing (WGS) analysis (“DNA”)

- *Biochemical and “Omics” Assessments*

Biochemical and “omics” assessments consist of the following elements, using peripheral blood samples, and potentially urine, stool or saliva samples.

- Whole genome methylation analysis (“DNA methylation”)
- Whole transcriptome sequencing from circulating mononuclear cells (mRNA and miR)
- Proteomics profiling
- Metabolomics profiling
- Conventional biomarker analysis
- Urine analysis and profiling

- *Non-Invasive Imaging Assessments*

Non-invasive imaging assessment consists of the following elements, as directed, and determined by the Medical history and PE and biochemical and “omics” assessment, as described above. Imaging will follow the schedule in the table below, with an “x” indicating all participants and an “[x]” indicating imaging needed for risk-specific participants. Any deviation from the average population may trigger a dedicated organ specific MRI. Imaging may also be done at 18-, 24- and/or 36-month visits, depending on Medical history and PE at each visit, following the schedule at 6 or 12 months.

Imaging Procedure	Baseline	6 mos	12 mos
CT of head	x		
CT Angiogram of head/neck/face/sinus/orbits	x		
MRI of brain with and without contrast	x		x
MR Angiogram of head/neck time of flight			x
MRI of brain without contrast		[x]	
CT of chest, abdomen, and pelvis - mixed A/V	x	[x]	[x]
CT of chest, abdomen, and pelvis - venous only		[x]	x
MRI of spine without contrast (cervical/thoracic/lumbar)	x		x

 WOCBP include any female who has experienced menarche or is 10 years of age or older and who has not undergone successful surgical sterilization (hysterectomy, bilateral tubal ligation, or bilateral oophorectomy) or is not postmenopausal (defined as amenorrhea >12 consecutive months in women 50 years of age and older).

X-rays of extremities	x	[x]	x
Ultrasound (reproductive organs/bladder)	x	[x]	x

- *Functional Assessments (determined by the Medical history and PE, described above)*
  - VO2-max functional testing (maximum oxygen consumption)
  - Non-invasive endothelial function testing
  - Electroencephalogram (EEG)
  - Electromyography (EMG)
  - Ophthalmologic examination for vision preservation and other pathology
  - Optional: sleep study
- *Wearables and Quantified Self Assessments (determined by the Medical history and PE, described above)*
  - Ambulatory Electrocardiogram (ECG) monitoring (Apple Watch, ePatch or similar)
  - Continuous glucose monitoring
  - Oura ring (may obviate the need for formal sleep study), or similar product(s) measuring heart rate (HR), heart rate variation (HRV), sleep duration, sleep stage

## 4. Benefit/Risk Assessment

### 4.1. Potential Risks

The potential risks of the Puer study are minimal. The Puer study does not prescribe any pharmaceutical or medical device-based interventions. Information collected from the genomic analysis, comprehensive “omics” analysis, non-invasive imaging and functional assessment will be shared with the individual and, if desired, with the health care provider of choice of the individual. Any potential treatment decision of further diagnostic evaluation-related decision will be made by the individual and their chosen health care provider.

Accordingly, any potential risks of the Puer study are only related to the comprehensive evaluation. For comprehensive biochemical and “omics” profiling, individuals will undergo blood draw through venipuncture. The risks of blood draw and venipuncture are minimal and can be mitigated. AEs that may be associated with venipuncture and that must be included in the informed consent include:

- Pain
- Bruising
- Bleeding at the puncture site
- Fainting
- Inflammation of the vein

Individuals will also undergo MRI. MRI is a safe, non-radiation-based modality and when contraindication to MRI are adequately assessed, MRI examination does not pose any risk to the participants. Standard screening for contraindications to MRI examination will be performed at the imaging center, using the centers’ policies and procedures for screening to identify contraindications to MRI examinations. Gadolinium-based contrast agents may be administered in connection with the MRI examination. Gadolinium-based contrast agents have been associated with potential risks, including rare anaphylactic reactions and necrotizing systemic fibrosis (American College of Radiology, 2021).

The use of gadolinium contrast agents may be associated with anaphylactic reaction in 0.001% to 0.01% of cases, and gadolinium contrast agents have also been associated with nephrogenic systemic fibrosis (NSF) in patients with compromised renal function. Based on the 2021 ACR Manual on Contrast Media, any adverse event rate with gadolinium-based contrast media (“GBCM”) ranges from 0.07% to 2.4%. Most reactions are mild and physiologic. Allergic-like reactions are uncommon and vary in frequency from 0.004% to 0.7%. Severe life-threatening anaphylactic reactions are exceedingly rare (0.001% to 0.01%).

Individuals will also undergo CT. CT is a safe imaging method that includes exposure to ionizing radiation with or without contrast agents. The contrast is either given orally, rectally or intravenously. This contrast material can rarely cause medical problems or allergic reactions. Most of these reactions are mild and result in a rash or itchiness. In rare instances, an allergic reaction can be serious, even life-threatening.

During an abdominal ultrasound exam, a trained technician will glide a small device over the participant’s abdomen to take pictures of the tissue under the skin. There are no known side effects from taking part in an abdominal ultrasound exam. Ultrasound tests do not involve radiation and they do not penetrate the skin.

Due to the risk of imaging radiation exposure to a fetus, WOCBP must not be pregnant at any visit.

Individuals will also undergo x-ray imaging. X-ray is an imaging method that includes exposure to a low amount of electromagnetic radiation to take pictures of structures in the body, such as bones.

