Objectives	

• The primary objective is to establish a baseline profile for individual healthy study subjects using various modalities and monitor them longitudinally to identify deviations that develop over time and may be relevant to human health and longevity. The secondary objective is to identify the modality that has the highest impact on the identification of deviations from baseline profile.

Adverse Event (AE) Monitoring	Adverse events associated with the study procedures, of venipuncture, non-invasive imaging and functional tests will be reported, although they are expected to be limited due to the nature of these common procedures.

Inclusion Criteria	To participate in the study, patients must meet the following criteria;						
	
 
1. Male or non-pregnant female; age 18 to 90.
 
2. Absence or presence of any medical history or any signs or symptoms of any disease.
 
3. Women of childbearing potential (WOCBP) must have a negative urine pregnancy test (UPT) at all visits.
 
						
Exclusion Criteria	Patients who meet any of the following criteria will be excluded from study participation;						
	
 
1. Unwillingness or inability to participate in the study
 
2. Unwillingness or inability to provide written Informed Consent Form
 
3. WOCBP with positive pregnancy test at enrollment or at any visit
 
						
Study Schedule	Event	Baseline Visit	6-Month Visit $\pm$ 1month	12-Month Visit $\pm$ 1month	18-Month Visit $\pm$ 1month	24-Month Visit $\pm$ 1month	36-Month Visit $\pm$ 1month
	Informed Consent	X					
	Review of Inclusion/Exclusion Criteria	X					
	Medical history and physical exam	X	X	X	X	X	X
	UPT for WOCBP	X	X	X	X	X	X
	Whole Genome Sequencing Analysis	X					
	Biochemical/Omics Analysis	X	X	X	X	X	X
	Non-Invasive Imaging	X	X	X	X	X	X
	Functional Assessments (as needed)		X	X	X	X	X
	Wearables and Quantified Self Assessments (as needed)		X	X	X	X	X
	Adverse Event Monitoring	X	X	X	X	X	X

1. UPTs must have a minimum sensitivity of 25 mIU  $\beta$ -hCG/mL.

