## **4.2. Potential Benefits**

Participants may not derive any benefit at all from participating in the study. At the same time, the extensive genetic, biochemical, and non-invasive imaging evaluation may uncover unknown genetic susceptibilities and/or early identification of variance and deviations from a study subject's baseline profile that may be worthy of further evaluation and testing by the study subject's primary care physician, providing some potential benefits to participants.

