## 5. Adverse Events

### 5.1. Definitions

An Adverse Event (AE) is a noxious and unintended event observed in, or reported by, a participant who is participating in (or has participated in) a clinical study, and/or received study medication, an experimental device, or study-related procedure. The event may be related temporally either to immediate or long-term use of a drug, device, or procedure. It may not necessarily be caused by a drug, device, or procedure. Any event meeting these criteria shall be considered an adverse event, regardless of whether or not it is considered study related. A pre-existing condition that worsens during the trial is considered an AE.

The following events will be considered as adverse events:

- Event directly related to study procedure
- Unintended event as a result of non-standard of care study tests, medications or procedures

A Serious Adverse Event (SAE) is defined as one that is fatal or immediately life-threatening, severely or permanently disabling, requires or prolongs in patient hospitalization, a congenital anomaly, cancer or overdose (intentional or accidental); or suggests a significant hazard, contraindication, side effect, or precaution. All SAEs will be followed by the investigator through trial end until resolution or until reaching a clinically stable status per the investigator's discretion.

The following adverse events will be handled as serious even if they do not meet the above criteria for designation as serious:

- Death
- Congenital abnormality
- Hospitalization
- Life threatening illness
- Intervention to prevent permanent damage

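### Section 4.1 limits the study's risks to the evaluation itself while 4.2 counts follow-up of findings as a benefit, and 5.3 has no causality category for harm from that follow-up

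*Protocol*

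**What the plan says.** **Risk.** Protocol section 4.1 states that the information collected "will be shared with the individual and, if desired, with the health care provider of choice of the individual". It adds: "Any potential treatment decision of further diagnostic evaluation-related decision will be made by the individual and their chosen health care provider". From this it draws the conclusion that "any potential risks of the Puer study are only related to the comprehensive evaluation". The risks then described are those of venipuncture, MRI and gadolinium, CT and its contrast, ultrasound and x-ray.

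**Benefit.** Section 4.2 first warns that participants may gain nothing. It then says that findings "may be worthy of further evaluation and testing by the study subject's primary care physician, providing some potential benefits to participants". Section 1.2 expects deviations to inform lifestyle changes and other interventions. Section 4.3 concludes that the balance favours taking part because the risks already described are minimal or negligible.

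**Yield.** The main endpoints in 2.2 count new deviations at set times and by modality.

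**AE scope and attribution.** The synopsis says: "Adverse events associated with the study procedures, of venipuncture, non-invasive imaging and functional tests will be reported". The first paragraph of 5.3 is narrower: "Any AEs are associated with blood draw/venipuncture and MRI examinations that may or may not include Gadolinium-based contrast agents will be reported". Section 5.1 defines an AE whether or not it is study related, and its list of qualifying events includes "Unintended event as a result of non-standard of care study tests, medications or procedures". The second paragraph of 5.3 puts every AE on the case report form (CRF). The one attribution detail it asks for is the "causality relationship to the study procedure (if applicable").

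**The concern.** The inference in 4.1 turns on who takes the decision, but attribution of harm turns on what set the chain in motion. If a participant has an invasive test only because the study flagged a deviation, a complication of that test is a consequence of taking part, even though an outside provider ordered it. The protocol accepts this reasoning when it counts benefit and drops it when it counts risk.

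Two things are at stake. The benefit/risk statement in 4.3 weighs a pathway whose benefits are included and whose harms are not. And the safety data, collected at up to 20 sites, may treat the same event differently from site to site, because the protocol does not say whether such harm is reportable or how it is to be attributed. A reader of the final report would then see deviation counts by modality with no corresponding count of harm from acting on them.

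**Working it through.** The protocol states no figure on this point and plans no hypothesis test (section 7), so there is nothing to recompute. The check is to trace one case through the text.

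**Case.** A study scan or blood test shows a new deviation. The participant's own provider orders an outside procedure to investigate it. The procedure causes a complication.

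**On the yield and benefit side:**

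1. Section 2.2: the deviation counts in the total of new deviations and in the count for the modality that found it.
2. Section 4.2: the outside evaluation is the kind of follow-up listed as a potential benefit.

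**On the risk side:**

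3. Section 4.1: the complication is outside the stated risks, which are confined to the evaluation.
4. Section 4.3: the conclusion relies on the risks as described, so the complication is absent from it too.

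**In AE reporting:**

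5. Synopsis: the complication does not arise from venipuncture, imaging or a functional test. Read literally, it is not reportable.
6. Section 5.3, first paragraph: the scope is blood draw and MRI only. Again not reportable on a literal reading.
7. Section 5.1, general definition: an unintended noxious event in a participant is an AE regardless of relatedness. Reportable.
8. Section 5.1, list of events: it is not directly related to a study procedure. It could fall under the second item, if a result of study tests is taken to include an indirect result. Open.
9. Section 5.3, second paragraph: it goes on the CRF. The causality item asks only about the study procedure and allows for the item not applying. No response describes harm from follow-up of a finding.

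**Result.** Steps 5 and 6 leave the event out. Steps 7 and 9 record it with attribution undefined. Step 8 could admit it as a consequence of study tests. No section says which reading governs, and none links the event to the finding that prompted it. The finding is counted under every reading.

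**The case against.** The strongest case against is that the protocol already captures much of this. Participants are asked open questions at each contact, all AEs go on the CRF, all serious AEs go to the IRB, and hospitalization is handled as serious (5.1, 5.3). The principal investigator reviews study-related events (5.4). Section 2.4 counts unscheduled urgent care and emergency visits and unscheduled admissions to 36 months. An organ-specific MRI triggered by a deviation appears among the study's own imaging in 3.3.2, so its AEs fit the existing causality item.

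Most of this stands, and it limits the point to work-up and treatment led by outside providers. It does not remove it. The 2.4 counts carry no link to a study finding and leave out planned procedures, and serious-event reporting does not settle attribution.

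A reader might infer that such harm is reported as unrelated. The protocol does not say so. It leaves the classification open, and the second listed item in 5.1 could make it related.

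A reader might also infer that AE coding is what prevents the study's net impact from being read. That is not supported: the study is descriptive with no comparison group described, and better AE coding would not change that.

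Finally, a reader might set assumed complication numbers against the severe gadolinium reactions implied by 4.1. With up to 10,000 participants and two scheduled contrast brain MRIs each, there are 20,000 administrations, and 0.001% to 0.01% gives 0.2 to 2 severe reactions. But 4.1 also gives a rate for any adverse event of 0.07% to 2.4%, or 14 to 480 events, and no rate at all for complications of follow-up. A comparison with the severe reactions alone would be selective and would show little.

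**Conclusion.** The point holds in a limited form. Section 4.1 draws a wrong conclusion about the scope of risk, 4.2 treats the same pathway as a source of benefit, and 4.3 builds on both. Sections 5.1 and 5.3 and the synopsis give differing AE scopes and no causality category for harm from finding-prompted care led by an outside provider. Such harm may go unreported or be recorded without attribution to the study.

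This is a stated scope error and an internal inconsistency, not a detail that can be left to an analysis plan. It should be corrected, but it affects no test, sample size or main endpoint count. Its size cannot be given because the documents contain no rate of follow-up procedures or of their complications. The verdict rests on the protocol text alone: the AE form and the consent pages are not available, so what the form already asks and what participants are told cannot be judged.

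**What to change.** 1. In 4.1, replace the statement that confines risk to the evaluation with wording that risks also include harm from further testing or treatment prompted by study findings. Carry this into the benefit/risk conclusion in 4.3.
2. Reconcile the AE scope statements in the synopsis, 5.1 and both paragraphs of 5.3, so that all sites apply one rule and it is clear whether harm from finding-prompted care is reportable.
3. Add one response to the causality item in 5.3: *related to follow-up testing or treatment prompted by a study finding*. Report its count descriptively beside the deviation counts, and by modality only where the prompting modality has been recorded.

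**Cost.** A sentence each in 4.1 and 4.3, an edit to the AE text, one added response category and one descriptive count. The investigator makes one more attribution judgement per AE, and the benefit/risk statement becomes slightly less favourable. A full breakdown by modality would cost more, since each event would have to be linked to a specific deviation. Section 6.1 does not clearly cover outside providers' work-up records, so the count would rest largely on what participants report at each contact. No procedure or visit is added.
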